# 8 Statistical Considerations

# 8.1 Study Endpoints

- Describe the primary and secondary study endpoints.
  - The primary outcome measure of this proposal is lower neonatal adiposity at birth in the LIPP group relative to: 1) the usual care/control group. As secondary outcomes we anticipate that prior to a subsequent pregnancy, LIPP will produce significant improvement (absolute and percent changes) in maternal weight and body composition, and more importantly improved insulin sensitivity,  $\beta$ -cell function, incretin response to glucose, lipid and inflammatory biomarkers, compared to the Control group. We also expect reduced insulin resistance, umbilical cord lipids and inflammatory profiles in babies born to LIPP subjects compared to Controls.
- Describe any primary or secondary safety endpoints. The risk of having a small for gestational age baby or preterm delivery will be followed closely in the intervention group, as this is a theoretical risk.

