#### 8.2 Statistical Analysis

• Describe the statistical analyses that will be performed for this study **Statistical Analysis** 

The primary analyses of Specific Aim 1a will be intent-to-treat comparisons of the LIPP and Control groups in regard to changes in maternal insulin sensitivity, BMI, and fat mass. The comparisons will be performed first with two-sample t-tests at  $\alpha$ =0.05. Should any imbalance of confounding factors in the groups be recognized, linear regression models that include significant differences (e.g. GDM) would be used to perform covariate adjustments. Based on our 1-year postpartum follow-up studies (62,63), we will have 90% power to detect an absolute or covariate-adjusted improvement in insulin sensitivity of 30% and an 80% power to detect an improvement as small as 25% in the LIPP vs. Control group. Corresponding 95% confidence intervals (95% CI) for the absolute or covariate-adjusted differences or percent improvements in insulin sensitivity between groups will be reported. We estimate the standard deviation (SD) of change in BMI from randomization until subsequent pregnancy to be 5.1 kg/m2. We will have 90% power to detect an absolute or covariate-adjusted difference in BMI of 2.6 kg/m2 and 80% power to detect a difference of 2.26 kg/m2 and 90% power to detect an absolute or covariate-adjusted difference in fat mass of 5.9 kg and 80% power to detect a difference of 5.1 kg between groups prior to the second pregnancy. The primary analysis for Specific Aim 1b is an intent-to-treat comparison of LIPP versus Control neonates with respect to fat mass at birth. The comparison will be performed using a two-sample t-test at  $\alpha$ =0.05. Linear regression will be performed, which will include weight (body composition measures) of the subject's index child as a covariate. Should any imbalance of confounding factors (for example gestational age) in the groups be recognized, linear regression models will be used to perform a covariate adjustment. Based on our preliminary data, we estimate the SD of neonatal fat mass between the LIPP and Control groups to be no more than 225 g. With at least 50 women in each group, (assuming a 50%) dropout), the t-test or linear regression will have 90% power to detect an absolute or

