covariate-adjusted difference of 146 g fat mass between groups. We have 80% power to detect an absolute or covariate-adjusted difference as small as 126 g fat mass between groups. Corresponding 95% CI for the absolute or covariate-adjusted difference in neonatal fat mass between groups will be reported. For secondary analyses, we will be using the same

statistical approach. Based on our preliminary data, we estimate the SD of birth weight to be 700 g; with 50 neonates in each group we will have 90% power to detect an absolute or covariate-adjusted difference of 455 g in birth weight and 80% power to detect a 393g difference between groups. Additional secondary analyses will include umbilical cord cytokines. Comparisons will be performed using a two-sample t-test at a significance level of  $\alpha$ =0.05; however, Mann-Whitney U tests or log transformations will be employed if data are not normally distributed. Linear regression models, including confounding factors, will be used to perform covariate adjustments. Based on our published data (80), we estimate the standard deviations of umbilical cord IL-6 and CRP to be 3.4 pg/ml and 7,900 ng/ml, respectively. With 50 women in each group, we will have 90% power to detect an improvement in IL-6 and CRP levels of 50% and 42%, and 80% power to detect an improvement of 42% and 36%, respectively.

The primary goal of Aim 2 is to determine the effect of lifestyle intervention prior to pregnancy on placental mitochondrial fatty acid oxidation at term. We hypothesize that placental  $\beta$ -oxidation will be higher in the LIPP group. We will conduct an intent-to-treat analysis using two sample t-test or non-parametric Wilcoxon rank-sum test to assess differences between groups. Regression analysis will be used to assess the association of placental  $\beta$ -oxidation and enzyme activity with maternal inflammatory cytokine levels and insulin resistance in early pregnancy, along with neonatal fat mass with adjustment for gestational age and gender. Descriptive statistics, such as mean, median and range will be calculated for all variables. Power and sample size analysis based on our preliminary mitochondrial  $\beta$ -oxidation data in obese women (38±14 nmol/mg/hr) showed that a sample size of N=18/group achieves 80% power to detect a difference of 25% between groups using a two-sample t-test with a significance level of 0.05.

• *Provide a power analysis.* These are included in the statistical analyses.

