## 8.3 Number of Subjects

- If this is a multicenter study, specify the number of subjects to be enrolled in total across all sites. 220.
- Specify the number of subjects to be enrolled at the Tufts site. Subjects who sign an ICF are considered "enrolled". For studies that have a separate screening ICF, this number is the number of subjects who sign a screening ICF. 100
  - Provide the rationale for enrolling this number of subjects at the Tufts site.
     This is approximately 50% of the study recruitment goals of 200. In addition to the already recruited participants in Cleveland and Baton Rouge, the Boston sites anticipate to recruit the remaining subjects to meet the goals.
  - Estimate the number of subjects expected to be enrolled at the Tufts site (i.e. sign the screening or study ICF) as well as the number needed to complete the study at the Tufts site.
     We anticipate recruiting 100 subjects in the Greater Boston area and expect a 40 to 50% dropout for various reasons.
  - If a large number of withdrawals and/or dropouts are expected, explain why.
     It is not unusual for a lifestyle intervention study lasting over a number of years to have a 40% dropout rate. This has been addressed in the statistical analysis.

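### The primary test is labelled intent-to-treat, but it compares only women with a delivered, measured neonate, and the expected 40–50% loss is handled only by a smaller n in the power statement

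*Combined protocol and SAP*

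**What the plan says.** Section 8.1 gives the outcome: "The primary outcome measure of this proposal is lower neonatal adiposity at birth in the LIPP group". Section 8.2 gives the analysis: "The primary analysis for Specific Aim 1b is an intent-to-treat comparison of LIPP versus Control neonates with respect to fat mass at birth". It continues: "The comparison will be performed using a two-sample t-test at" the 0.05 level. A linear regression with the index child's weight or body composition as covariate follows, and other confounders are added if an imbalance is noticed.

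The sample size in the same section rests on two statements: "we estimate the SD of neonatal fat mass between the LIPP and Control groups to be no more than 225 g" and "With at least 50 women in each group, (assuming a 50%) dropout), the t-test or linear regression will have 90% power". The detectable differences are 146 g (90% power) and 126 g (80% power).

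Section 8.3 expects 40 to 50% dropout at the Boston sites and says of it: "This has been addressed in the statistical analysis".

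Section 4.3 (Withdrawal of Subjects) has four relevant provisions:
- Women who have not conceived by 21 months postpartum stay in the study and are followed until pregnancy or study end.
- Women who conceive within 16 weeks of randomisation are asked to withdraw.
- Missed assessments and missed training sessions are given as reasons for which subjects have been asked to withdraw.
- Demographic data on withdrawn women will be kept and compared with those of compliant women, to look for compliance bias.

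**The concern.** An intent-to-treat comparison keeps the protection of randomisation because everyone randomised is compared in the assigned arm. That cannot happen here. Women who do not conceive, are withdrawn, or whose neonate is not measured have no primary outcome. Section 8.2 names no analysis set, no missing-data method and no sensitivity analysis for them.

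Membership of the analysed set is settled after randomisation and can differ by arm:
- Supervised training sessions exist only in the LIPP arm, so withdrawal for missing them can act only there.
- The timing of conception decides both early withdrawal and whether a neonate is born before the study ends. Weight loss could plausibly affect it.
- Visit payments differ. Section 4.4.3 gives $490 over seven visits in LIPP, where most of the value is in kind, and up to $2,250 in usual care.

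If the arms differ in who contributes a neonate, and those women differ in expected neonatal fat mass, the observed difference mixes a selection effect with the effect of the intervention. Lowering n protects power against loss. It does nothing about this.

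**Working it through.** **1. Reproduce the plan's power.** Inputs from Section 8.2: SD 225 g, 50 per arm, α = 0.05. Sidedness is not stated, but two-sided reproduces the figures.

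- SE of the difference = 225 × √(2/50) = 45.0 g.
- At 146 g: 146/45 − 1.96 = 1.284, power 90.1% (89.5% with the t distribution).
- At 126 g: 126/45 − 1.96 = 0.84, power 80.0% (79.2% with t).

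Both stated figures reproduce. With 100 per arm the SE would be 225 × √(2/100) = 31.8 g and power 99.6% and 97.7%. The stated power therefore belongs to a test on the women left after loss. The documents never use the term complete-case, but no other reading fits the test and the n.

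**2. How many lack the outcome.** 50/(1 − 0.5) = 100 per arm, or 200 in total, which matches the recruitment goal in Section 3. Section 8.3 also gives 220 across sites. Applying the Boston dropout range to both totals:

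| Total N | Loss | With outcome, per arm | Without outcome, total |
|---|---|---|---|
| 200 | 40% | 60 | 80 |
| 200 | 50% | 50 | 100 |
| 220 | 40% | 66 | 88 |
| 220 | 50% | 55 | 110 |

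**3. Where dropout is addressed.** In Section 8.2 the only mention is "With at least 50 women in each group, (assuming a 50%) dropout", inside the power statement. The comparison promised in Section 4.3 does not appear in Section 8.2. It covers demographics only and women who withdraw. Women who never conceive are not withdrawn, so it misses them.

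**4. Illustrative size.** The documents give neither conception or retention by arm nor the fat mass expected in the differing women, so these inputs are assumptions. Suppose a fraction p of controls contributes a neonate and p + d of LIPP women do, and the extra d have neonates differing by D grams. There is no true effect, and 100 women are randomised per arm.

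Shift in the LIPP mean = d/(p + d) × D. SE = 225 × √(1/n₁ + 1/n₂). With k = shift/SE, two-sided type I error = P(Z > 1.96 − k) + P(Z < −1.96 − k).

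| Controls vs LIPP contributing | D | Shift | SE | Shift/SE | Type I error |
|---|---|---|---|---|---|
| 50% vs 60% | 50 g | 0.1/0.6 × 50 = 8.3 g | 43.1 g | 0.19 | 5.4% |
| 50% vs 60% | 100 g | 16.7 g | 43.1 g | 0.39 | 6.7% |
| 50% vs 60% | 150 g | 25.0 g | 43.1 g | 0.58 | 8.9% |
| 50% vs 70% | 100 g | 0.2/0.7 × 100 = 28.6 g | 41.7 g | 0.69 | 10.5% |

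Against the 126 g target these shifts are 7% to 23%.

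**The case against.** Several points on the other side stand.

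- A reader might infer that nothing is planned to find out who is missing. That is not so: Section 4.3 plans the demographic comparison. It is narrow, but it exists.
- A reader might infer that half of all randomised women will be missing. The documents do not say this. Section 8.3 counts a woman as enrolled when she signs consent, and Section 4.3 provides for withdrawal because of pregnancy before randomisation, so part of the loss may precede randomisation. The wording of at least 50 per group makes 50% a planning ceiling.
- A reader might take the early-pregnancy withdrawal rule to apply only to the intervention arm, because it refers to a LIPP subject. The same sentence covers pregnancies before randomisation, so it means a trial subject. The rule is common to both arms; only its frequency could differ.
- The plan does adjust. The index-child measure is already a covariate, and randomisation is stratified by overweight versus obese and by breastfeeding status (Section 8.5).
- The plan limits loss. Entry requires planning a pregnancy within 24 months, women needing assisted reproduction are excluded, non-conceivers are telephoned monthly, and neonates may be measured at home or by anthropometry.
- The sentence itself refers to neonates and the power statement discloses the dropout, so an attentive reader can see who is analysed.
- The assumed shifts are well under one standard error, and the largest assumed D (150 g) exceeds the 146 g target.
- Fat mass is undefined, not missing, when no pregnancy occurs. Inverse-probability weighting cannot supply it.

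These points limit the size of the concern and shape the remedy. None supplies an analysis set, a by-arm account of who is measured, or a sensitivity analysis.

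**Conclusion.** The concern holds in this form. The intent-to-treat label claims a property that the comparison does not have, and the statement that dropout is dealt with in the analysis is met only by a reduced n. The existing check is not stated to be by arm, leaves out women who never conceive, and does not bear on the primary estimate.

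The documents do not show that the arms will differ in who contributes a neonate, or that the result will be biased. A reader might infer from the illustration that selection could by itself produce a finding of the target size. It does not show that: the shifts are 8–29 g, or 0.2–0.7 standard errors, with type I error about 9–10% only in the larger cases. All of this rests on assumed contribution rates and assumed differences in fat mass. The point is a moderate weakness that should be corrected before the unblinded analysis; it does not invalidate the design.

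**What to change.** 1. In Section 8.2, describe the primary comparison as by randomised arm among women with a delivered, measured neonate. Correct the Section 8.3 statement on dropout to match.
2. Report conception, delivery and neonatal measurement by arm, with 95% confidence intervals for the differences. Extend the Section 4.3 comparison so that it is by arm, includes women who never conceive, and uses the baseline metabolic data as well as demographics.
3. Make the primary model a pre-specified regression on arm, the two randomisation strata (overweight/obese and breastfeeding status), site and the already planned index-child measure. This replaces adjustment triggered by observed imbalance.
4. Add one sensitivity analysis that weights measured women by the inverse of their modelled probability of being measured. State that it assumes baseline data explain who is measured, and that it does not define an outcome for women who never conceive.

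The cost is a weaker label, a longer results table and a little more analysis. The strata, site and baseline assessments are already collected, so no visit, procedure or sample size changes.

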# 🗹 Yes 🛛 No

If **Yes**, describe the following:

- *The randomization procedures, including the ratio of subjects randomized to each study arm.* Yes through a computer generated randomization stratified for overweight vs. obese and breastfeeding status.
- *The blinding procedures if the study will be blinded.* N/A, only the statistician analyzing data will be blinded.

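### Neonatal fat mass: a valid but unadjusted primary t-test gives up available precision, and the imbalance rule permits adjustment for gestational age, which arises after randomisation

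*Combined protocol and SAP*

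**What the plan says.** Section 8.2 introduces the endpoint with "The primary analysis for Specific Aim 1b is an intent-to-treat comparison of LIPP versus Control neonates with respect to fat mass at birth". The next sentence gives the method: "The comparison will be performed using a two-sample t-test", at a 0.05 level. Two regressions follow:

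- One is unconditional: "Linear regression will be performed, which will include weight (body composition measures" of the index child as a covariate. The text does not settle whether that means weight or another body composition measure.
- One is conditional: "Should any imbalance of confounding factors (for example gestational age) in the groups be recognized, linear regression models will be used" for a covariate adjustment.

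Neither is labelled supportive. The power sentence says "the t-test or linear regression will have 90% power to detect an absolute or" covariate-adjusted difference of 146 g. The reporting sentence reads "Corresponding 95% CI for the absolute or covariate-adjusted difference in neonatal fat mass between groups will be reported".

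Section 8.5 describes "computer generated randomization stratified for overweight vs. obese and breastfeeding status". Neither factor is named as a covariate in any model in section 8.2.

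Three other places bear on gestational age. Section 5.1 puts randomisation about three months after the index delivery, before the pregnancy that yields the outcome. Section 4.1 already restricts the index pregnancy to full term. Section 8.1 states "The risk of having a small for gestational age baby or preterm delivery will be followed closely in the intervention group" and calls this a theoretical risk.

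**The concern.** There are two separate issues.

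**Precision.** The plan stratifies on two factors and plans to use an index-child covariate, but the test that most naturally decides the primary comparison uses none of them. With about 50 neonates per arm expected after 50% dropout, any variance that these explain is worth recovering.

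**The meaning of the adjusted estimate.** The trigger treats gestational age as a possible confounder. Because the index pregnancy had to be full term, the natural reading is the gestational age of the study neonate, which is determined after randomisation. In a randomised comparison it cannot confound the treatment effect, but it can lie on the path from treatment to fat mass. The trigger is also most likely to fire when the intervention has changed gestation, which is when adjustment removes part of the effect of interest. Since the plan allows either an absolute or a covariate-adjusted difference to be reported, such an estimate could be presented as the trial's result.

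**Working it through.** **Inputs from section 8.2:** 50 per arm, SD 225 g, alpha 0.05 (taken as two-sided, which reproduces the plan's figures), target differences 126 g and 146 g.

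**Assumed, because the documents give no values:** index-child correlation r from 0 to 0.5; gestational-age SD 1.3 weeks; 30, 50 or 80 g of fat per week of gestation; trigger at p<0.05.

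**1. The plan's own figures.** Standard error = 225 × √(2/50) = 45 g. Noncentrality is 126/45 = 2.80 and 146/45 = 3.24. The normal approximation gives 80.0% and 90.1% power; the noncentral t with 98 df gives 79.2% and 89.5%. The plan's figures are reproduced.

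**2. One model with arm, two strata and one index-child measure.** There are 100 − 5 = 95 df, and residual SD = 225 × √(1 − r²). The strata are taken to explain nothing here, so any gain comes from the index-child measure alone.

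| r | Residual SD (g) | Power at 126 g | Difference at 80% power (g) |
|---|---|---|---|
| 0 | 225.0 | 79.2% | 127.4 |
| 0.2 | 220.5 | 80.8% | 124.8 |
| 0.3 | 214.6 | 82.8% | 121.5 |
| 0.5 | 194.9 | 89.3% | 110.3 |

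**3. Leaving out the strata.** If balanced strata explain a share R² of the variance, the true size of the nominal 5% t-test is about 2 × (1 − Φ(1.96/√(1 − R²))). For R² of 5, 10 and 20% this is 4.4, 3.9 and 2.8%. The test is conservative, so the cost is efficiency and not validity.

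**4. Gestational-age adjustment.** Suppose the total effect is a 126 g reduction and the intervention shortens gestation by k weeks. With b grams of fat per week, the adjusted estimate targets 126 − k × b. At k = 0.5 this is 126 − 15 = 111 g, 126 − 25 = 101 g and 126 − 40 = 86 g for the three slopes.

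The chance that the trigger fires is the power of a t-test on gestational age. At k = 0.5 the noncentrality is 0.5/(1.3 × √(2/50)) = 1.92, which gives 48%. At 0.25 week it is 16%, and at 0.1 week 7%.

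Simulation (20,000 trials per setting) for the case where the triggered regression *replaces* the t-test:

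| Shortening (weeks) | t-test power | Power if replaced (30/50/80 g per week) |
|---|---|---|
| 0.5 | 79–80% | 71 / 67 / 62% |
| 0.25 | 79% | 77 / 76 / 76% |
| 0.1 | 79–80% | 78 / 78 / 79% |
| 0 | 79% | 79 / 80 / 80% |

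At 0.5 week the adjusted estimate, when triggered, averaged 111, 101 and 86 g, as the arithmetic predicts. At 0.1 week the loss is under 1 point. With no shift there is neither bias nor loss.

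**5. Missing index-child values.** If 10% were missing (assumed) and those cases were dropped, 45 per arm would remain. Power at 126 g would then be 74.7, 76.4, 78.6 and 85.8% at r = 0, 0.2, 0.3 and 0.5, against 79.2% for the t-test on all 100. The model would lose unless r exceeded about 0.3.

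**The case against.** The strongest defence is that the plan does name a primary test. The t-test sentence follows the primary label directly. The parallel text for Aim 1a says that t-tests come first and regression follows if groups differ. On that reading the regressions are follow-on adjustments, and nothing is biased. This stands.

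A reader might infer more, in three ways that the documents do not support:

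- **That type I error is inflated.** This would need a rule that success on any of the analyses counts, and no section says so. Section 8.5 also blinds the analysing statistician. That does not stop a choice between p-values, but it limits selection in favour of the intervention.
- **That the triggered regression replaces the t-test.** The text neither states nor excludes this, so the replacement rows in the working are conditional on a reading the plan does not adopt.
- **That imbalance has no criterion at all.** Aim 1a speaks of significant differences. This implies a significance criterion, although no level is given and it is not repeated for Aim 1b.

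Two further points are fair. The documents do not show that breastfeeding status after the index birth predicts the next neonate's fat mass, so the gain from the strata may be nil. The index-child covariate may also be incomplete: the visit schedules in section 5.1 list no index-child measurement, and the Baton Rouge addendum describes recruitment through web advertising, flyers and community events.

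What remains is that the decisive test omits information the plan intends to use, and that the plan permits an adjustment for a post-randomisation variable and the reporting of an adjusted difference.

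**Conclusion.** The primary t-test is valid and its power statement is correct. This is a cheap improvement, not a repair of a faulty test.

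The gain from one pre-specified model is about 2, 4 or 10 percentage points of power at 126 g for an index-child correlation of 0.2, 0.3 or 0.5, and nothing at zero correlation. These correlations are assumptions.

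The gestational-age adjustment should not stand as written. If the intervention shifts gestation, the adjusted difference is not the total effect on fat mass. Under the assumed slopes, a 0.5-week shortening takes 15 to 40 g off a 126 g effect. At 0.25 week the power loss, were the adjusted result to decide, is 2 to 4 points. At 0.1 week or less it is negligible. The plan calls preterm delivery only a theoretical risk, so the size of any shift is unknown.

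**What to change.** In section 8.2, for neonatal fat mass:

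1. Make one linear model primary whatever the observed balance. Its terms are arm, the overweight/obese stratum, the breastfeeding stratum, and one defined index-child measure (for example birth weight).
2. Keep women with a missing index-child value in the analysis, for example by single mean imputation of this baseline covariate with a missing indicator. Do not use complete-case deletion.
3. Report that model's arm difference and 95% CI as the single primary result, with the t-test as supportive.
4. Delete the imbalance trigger for this endpoint. Use gestational age only in a labelled sensitivity analysis, described as not estimating the total effect.

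The statistical cost is three degrees of freedom, or four with a missing indicator. If the covariates explain nothing, three degrees of freedom lower power at 126 g from 79.17% to 79.15%, about 0.03 point. The practical cost is obtaining the index-child values. The plan already commits to using them, but the documents do not show how they are collected or how complete they are, and this should be settled before the model is fixed.

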Specific Aim 2: To determine the molecular effects whereby lifestyle intervention initiated before pregnancy can improve placental mitochondrial lipid oxidation and accumulation. The working hypothesis is that lifestyle intervention before pregnancy will increase placental mitochondrial lipid oxidation and decrease lipid esterification/storage (Fig. 2). Isotope-

labeled fatty acid oxidation and esterification will be quantified in vitro in placental explants. We will measure markers of mitochondrial lipid metabolism and content using qRT-PCR and ELISA approaches. Placental lipids will be quantified and correlated with neonatal adiposity and maternal metabolism.

Impact of the study: Clinically, the proposal provides feasible methods to improve short and longterm metabolic health of obese women and their offspring. Scientifically, this study will provide fundamental insights into the physiological and molecular mechanisms underlying maternal pregravid metabolism and effects on maternal/placental physiology.

Specify which are the primary or secondary aims or objectives of this study as applicable. The primary objective is the main question. Secondary objectives are goals that will provide further information for the study

We have not developed secondary aims for the study. These will be considered once the primary study is underway and secondary funding is sought. For example, we are in preliminary discussions with [name] in the school of nutrition to look at any spillover effect of the LIPP study on other family members. These discussions are at the initial stages and have not yet been fully developed or sought additional research funds.

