# aliquots of specimens, where they will be stored, how they will be labeled, and what will happen to the samples after the study is over (e.g. will be destroyed).

Samples from CTRC or the HNRCA will be placed on ice and then brought to the MIRI during the 3 hour OGTT or fasting blood draw, or processed on site. Samples will be aliquoted in separate vials in the MIRI to avoid freeze thaw cycles. Samples will be bar coded using a unique identifier code for subject name and study visit. Samples not run real time, will be stored in -80°Cfreezers in the MIRI. Samples not used at the completion of the study will be destroyed. The cord blood samples at the time of delivery will be brought to the MIRI for processing (glucose), and then aliquots stored at -80°C for analysis of insulin, cytokines and lipids. Samples from the BWH Research Facility will be handled in a similar manner but in the BWH research lab.

The placentas obtained at the time of delivery will be fixed for histological analysis, submerged in RNA Later, or snap frozen in liquid nitrogen and stored at -80°C for molecular analysis. For a subset of the subjects, we will obtain fresh placental tissue for lipid metabolism activity assays.

After participants have completed the study, insulin, c-peptide, and incretin samples will be sent to the PBRC site for analysis. Similarly, inflammatory markers, other biomarkers as noted and placental samples, will be shipped to TMC or BWH for analysis. An MTA will be obtained from the respective sites prior to shipping.

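### Aim 2 power: 18 placentas per group give about 51% power for a 25% difference in beta-oxidation, not the stated 80%

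*Combined protocol and SAP*

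**What the plan says.** Section 8.2 makes placental mitochondrial fatty acid oxidation at term the main Aim 2 outcome, to be compared between groups by a two-sample t-test or a Wilcoxon rank-sum test. The hypothesis is directional: "oxidation will be higher in the LIPP group". The sample-size support is one sentence. It cites preliminary beta-oxidation of 38±14 nmol/mg/hr in obese women and states that this "showed that a sample size of N=18/group achieves 80% power to detect a difference of 25% between groups using a two-sample t-test" at a significance level of 0.05. It does not say whether the test is one- or two-sided, which group's mean the 25% refers to, or whether ±14 is a standard deviation.

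Two other places bear on how many placentas will supply this outcome. Section 3 (Specific Aim 2) says that isotope-"labeled fatty acid oxidation and esterification will be quantified in vitro in placental explants". Section 5.3, on specimen handling, says "For a subset of the subjects, we will obtain fresh placental tissue for lipid metabolism activity assays" and gives no number for that subset.

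**The concern.** A 25% difference is 9.5 nmol/mg/hr against a spread of 14, a standardised difference of about 0.68. Eighteen per group is too few to detect that with 80% power in a two-sample comparison.

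The sentence is the only power statement for one of the trial's two specific aims, and 18 per group is the only number in the documents that could guide the size of the fresh-tissue subset. If staff collect to that number, a real 25% effect would be missed about as often as it is found, and a null result could be misread as evidence against the placental mechanism. Fresh tissue not taken at delivery cannot be obtained later.

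**Working it through.** **Inputs, all from section 8.2:** mean 38, spread 14 (read as SD), difference 25%, n = 18 per group, two-sample t-test, alpha 0.05. Sidedness is not stated.

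**1. Which sidedness does the section use?** The neonatal figures in 8.2 can be checked at 50 per group. For fat mass (SD 225 g) the plan gives 90% power for 146 g and says "We have 80% power to detect an absolute or covariate-adjusted difference as small as 126 g fat mass between groups". For birth weight (SD 700 g) it says "with 50 neonates in each group we will have 90% power to detect an absolute or covariate-adjusted difference of 455 g", and 80% for 393 g. Exact (noncentral t) power:

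| Difference / SD (g) | Stated | Two-sided | One-sided |
|---|---|---|---|
| 126 / 225 | 80% | 79.2% | 87.2% |
| 146 / 225 | 90% | 89.5% | 94.3% |
| 393 / 700 | 80% | 79.4% | 87.3% |
| 455 / 700 | 90% | 89.6% | 94.3% |

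These figures fit only a two-sided test.

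**2. Aim 2 on the same basis.**
- Difference = 0.25 × 38 = 9.5; d = 9.5/14 = 0.679.
- Noncentrality = d × √(n/2) = 0.679 × √9 = 2.036, with 34 degrees of freedom.
- The two-sided critical value is 2.032, almost equal to the noncentrality, so power is close to one half: **50.7%**. The normal approximation gives 53.0%, and a simulation of 200,000 trials gave 50.8%.

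**3. Sample size for 80%.**
- Normal approximation: n per group = 2 × (1.960 + 0.842)² × (14/9.5)² = 34.1, so 35.
- Exact t: 35 per group gives 79.9% and 36 gives 81.0%. Hence about **36 per group**.
- Wilcoxon test on normal data (20,000 simulations): 48% at 18 per group, 79.9% at 37 and 80.7% at 38, so about 37 to 38 per group.

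**4. What 18 per group can detect.** At 80% power, two-sided, d = 0.961, so the difference is 0.961 × 14 = **13.5 nmol/mg/hr**, and 13.46/38 = 35%. For 9.5 to be detectable, the SD would have to be about 9.5/0.961 = 9.9.

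**5. Other readings of the sentence** (SD 14, 18 per group, exact t):

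| Reading of 25% | Difference | Two-sided power (n for 80%) | One-sided power (n for 80%) |
|---|---|---|---|
| 25% of 38 | 9.5 | 50.7% (36) | 63.7% (28) |
| 38 is 75% of the larger mean | 12.67 | 75.1% (21) | 84.5% (16) |
| 38 is 125% of the smaller mean | 7.6 | 35.3% (55) | 48.1% (43) |

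On a log scale (CV 14/38 = 0.368), a ratio of 1.25 gives 44.6% two-sided and 57.7% one-sided; a ratio of 1.333 gives 65.2% and 76.6%. If ±14 were a standard error from an assumed 5 to 40 samples, two-sided power for 9.5 would be 14% down to 6%. None of these two-sample readings comes within two points of 80% at 18 per group.

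**6. A possible source.** The one-sample formula, (1.960 + 0.842)² × (14/9.5)² = 17.05, rounds up to 18. That is the formula in step 3 without its factor of 2. This is an inference; the documents do not show the calculation.

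**7. Power for 9.5 by number assayed (two-sided).** 18 per group: 51%; 25: 65%; 30: 73%; 36: 81%; 50: 92%.

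**The case against.** The strongest reply concerns consequence rather than arithmetic. Nothing in the plan says that the Aim 2 analysis will stop at 18 per group. The visit schedule lists placental measurements at delivery without a cap, and 8.2 works with at least 50 women per group after dropout, where power is 92%. The endpoint is mechanistic: section 8.1 does not list it among the primary or secondary outcomes, and the trial's enrolment target does not rest on it. All of this stands. The harm depends on the subset size, which is a gap in the plan rather than proof of an underpowered aim.

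A second reply is that several inputs are unstated, so a single figure of 51% is too definite. It is right that 51% is not the floor: taking 38 as the higher mean, or ±14 as a standard error, gives less. Those readings widen the shortfall. The first is also unnatural, because 38 comes from obese women in preliminary data and the intervention is expected to raise oxidation. In the other direction, a one-sided test combined with 25% of the larger mean passes 80%, but it needs two unstated choices, departs from the two-sided basis of the neonatal figures and would have produced 16 rather than 18. A directional hypothesis does not by itself declare a one-sided test. An SD near 9.9 would also rescue the figure, but nothing in the documents supports one.

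**Conclusion.** The stated 80% is wrong as written. With ±14 as the SD, 25% taken of 38 and a two-sided test at 0.05, power at 18 per group is about 51%, and the sample size for 80% is understated by a factor of two (36 rather than 18). With ±14 kept as the SD and 38 as the lower mean, the two remaining unstated choices move power between 51% and 84% on the original scale, and none of the four combinations yields 18 per group for 80%.

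The error is confined to Aim 2 and leaves the primary endpoint and total enrolment untouched. Whether it costs the trial anything depends on how many fresh placentas are assayed: little if about 50 per group, about half the chance of detecting a true 25% effect if about 18. It should be fixed, but it does not threaten the trial's main conclusion.

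**What to change.** In section 8.2, state the sidedness, the mean to which the 25% refers and that ±14 is an SD (or supply the SD if it is not). Then restate the sentence along these lines: *with 18 per group, power is about 51% (two-sided, alpha 0.05) for a 25% difference (9.5 nmol/mg/hr, SD 14) and 80% for a difference of about 35% (13.5 nmol/mg/hr).*

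In section 5.3, give the planned number of fresh-tissue placentas per group. If the 25% target is kept, say that about 36 assayed placentas per group are needed, or about 37 to 38 if the Wilcoxon test is used (a figure that assumes normal data).

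The cost is one restated sentence, one added number and a less favourable stated power. No extra enrolment is needed if about 50 women per group complete, which rests on the 50% dropout assumed in 8.2 (section 8.3 gives 40 to 50%). More assays are needed only if the 25% target is kept and the intended subset is below about 36 per group.
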